#### e. Screen failure procedures

Subjects who discontinue following consent (i.e., post in-person questionnaires at recruitment) but prior to receiving the Connect-Home intervention or control will be considered screen failures. No additional data will be collected from the time of screen failure, but data collected prior to screen failure and reason for screen failure will be kept.

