**6. STUDY PROCEDURES**

The study team will use a limited waiver of HIPAA authorization to pre-screening for patient and caregiver eligibility during the SNF admission. The study team will recruit SNF patients and their caregivers in-person (or, when risk mitigation related to COVID-19 prevents in-person contact, we will recruit virtually, using an iPad and connection via ZOOM) within 10 days of their admission and will review the patient's medical record to confirm eligibility. The study team will obtain written consent (or, when risk mitigation related to COVID-19 prevents in-person contact, they will obtain verbal consent) of SNF patients and their caregivers. The study team will collect baseline data during the SNF admission. SNF patients and caregivers will receive the Connect-Home Plus intervention in the SNF and the SNF caregivers will receive the intervention after the SNF discharge in a home visit

with the home care nurse and in telephone calls with the dementia caregiving specialist in 30 days after SNF discharge. The study team will collect outcome data from the patient and caregiver (or from the caregiver only if the patient is not able to participate in data collection) in 7, 21, and 30 days after SNF discharge. The chart review of medical records will occur in 30 days after SNF discharge.

a. Screening/Baseline Visit procedures

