Connect-Home Plus is a two-step transitional care intervention: 1) SNF staff create an individualized Transition Plan or Care and prepare the patient with ADRD and caregiver to manage the patient's illness at home; and 2) within 3 days of discharge a home care nurse visits the patient and caregiver at home and within 30 days of SNF discharge, a dementia caregiving specialist calls the caregiver three times at home and helps them implement the written Transition Plan of Care. Both intervention steps focus on 6 key care needs to optimize patient and caregiver outcomes: 1) home safety and level of assistance; 2) advance care planning; 3) symptom management; 4) medication reconciliation; 5) function. See **Section 5** for additional detail.

c. Follow- up procedures (by visits)

Schedule of Activities for Patients:

See next page

Assessments and Procedures	Screen	Pre Discharge	Discharge	1-3 days post discharge	7 Days Post-Discharge (+ 10/- 3 days)	21 Days Post-Discharge (+/- 7 days)	30 Days Post-Discharge (+/- 7 days)
Informed Consent	X						
Confirm Eligibility	X						
Baseline interview		X					
Chart Abstraction					X		
Connect-Home in SNF		X					
Home Care Nurse visits				X			
CTM-15					X		
Satisfaction interview						X	
DEMQoL							X
Life Space Assessment							X
Chart Abstraction							X
Hospital and ED use assessment							X

Schedule of Activities for Caregivers:

Assessments and Procedures	Screen	Pre Discharge	Discharge	1-3 days post discharge	7 Days Post-Discharge (+ 10/- 3 days)	21 Days Post-Discharge (+/- 7 days)	30 Days Post-Discharge (+/- 7 days)
Informed Consent	X						
Confirm Eligibility	X						
Baseline interview		X					
Connect-Home in SNF		X					
Home Care Nurse visits				X			
Readiness for Caregiving assessment					X		
Dementia Caregiving Specialist calls				X	X	X	
Satisfaction interview						X	
DEMQoL-proxy assessment							X
Caregiver burden and distress assessment							X

d. Subject Completion/ Withdrawal procedures

All identifying information will be destroyed at the earliest possible time following completion of the study. In addition, data will be reported in aggregate form, without identifying information by site or individual. Publications arising from the study will not contain personal information.

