- Dementia Quality of Life-Proxy measure (DEMQOL-Proxy). When the patient is unable to rate their quality of life, the quality of life will be rated by their caregiver, using the Dementia Quality of Life-Proxy measure.(33) The score range is 31-124 with higher scores indicating better quality of life.
- Self-Reported Days of ED or Hospital Use 30 Days After Skilled Nursing Facility Discharge. Patient's days of acute care use will be measured using the self-reported number of combined number of days the patients pends in the Emergency Department (ED) or hospital in 30 days after SNF discharge.(19)
- Zarit Caregiver Burden Scale. Caregiver burden will be measured using the Zarit Caregiver Burden Scale, which includes 12 items on a five-point scale, measuring caregiver perceptions that "caregiving has an adverse effect on their emotional, social, financial, physical and spiritual functioning."(34) Scores range 0-48; higher scores are associated with depression and social isolation.
- Distress Thermometer. Caregiver distress will be measured using the Distress Thermometer, which includes 1 item on an 11-point scale, measuring negative affect (e.g., sadness and fear) related to caregiving for a severely ill person. Score ranges 0-10, with scores >4 associated with poor coping and depression.(35)

a. Safety Evaluations

- Study progress and safety will be reviewed monthly (and more frequently if needed). Progress reports will include patient and caregiver recruitment, retention/attrition, and adverse events. In addition, safety evaluation will include (1) whether adverse event rates are consistent with pre-study assumptions; (2) reason for dropouts from the study; (3) whether all participants met entry criteria; (4) whether continuation of the study is justified on the basis that additional data are needed to accomplish the stated aims of the study; and (5) conditions whereby the study might be terminated prematurely.
- An adverse event (AE) is any untoward medical occurrence in a subject temporally associated with participation in the clinical study or with use of the experimental agent being studied. An adverse finding can include a sign, symptom, abnormal assessment or any combination of these. A Serious Adverse Event (SAE) is any adverse event that results in one or more of the following outcomes:
  - Death
  - A life-threatening event
  - Inpatient hospitalization
  - A persistent or significant disability/incapacity

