### **Primary Endpoint**

The sample of 20 patients and their 20 caregivers is sufficient to determine feasibility (i.e., the extent that staff will be able to deliver components of the Connect-Home Plus as intended) and the acceptability of Connect-Home Plus (i.e., the perceptions of the patients and caregivers that the intervention is easy to use, helpful, and provides skills for care of the patient at home).

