### **Statistical Methods**

- Baseline data. Descriptive statistics will be used to analyze data collected in baseline surveys and chart reviews and describe patient clinical and non-clinical characteristics. Descriptive statistics will also be used to analyze baseline data collected from caregivers and describe nonclinical characteristics of caregivers.
- Efficacy Analysis. The study will not include an analysis of efficacy; rather, descriptive statistics will be used to describe the feasibility and acceptability of the intervention and to describe patient and caregiver outcomes in 30 days after SNF discharge. The primary outcome evaluation will use descriptive statistics to describe feasibility of providing the 8 intervention components identified in the feasibility chart review guide. The primary outcome evaluation will also use descriptive statistics to describe the acceptability of Connect-Home Plus. In addition, the secondary outcome evaluation will use descriptive statistics to describe preparedness for care after discharge (patient and caregiver); patient quality of life, functional mobility and acute care use; and caregiver burden and distress.
- Safety Analysis. Descriptive statistics will be used to describe patient and caregiver recruitment, retention/attrition, and adverse events.

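### Does calling every consented subject who leaves before the intervention a screen failure hide early losses from the retention description?

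*Combined protocol and SAP*

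**What the plan says.** All references are to the combined protocol and SAP.

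- **Section 6e (Screen failure procedures).** Subjects who discontinue after consent and the recruitment questionnaires, but "prior to receiving the Connect-Home intervention or control will be considered screen failures". It adds that "No additional data will be collected from the time of screen failure", but also that data already collected and the reason for the screen failure are kept.
- **Section 6 (opening text) and the schedules in Section 6c.** At recruitment the team "will review the patient's medical record to confirm eligibility". Both schedules place "Confirm Eligibility" in the Screen column, ahead of the baseline interview.
- **Section 7a (Safety Evaluations).** The review items include "reason for dropouts from the study" and, separately, "whether all participants met entry criteria".
- **Section 8 (Statistical Methods, Safety Analysis).** "Descriptive statistics will be used to describe patient and caregiver recruitment, retention/attrition, and adverse events". No denominator is given.
- **Section 8 (Primary Endpoint).** Feasibility means "the extent that staff will be able to deliver components of the Connect-Home Plus as intended".
- **Section 8 (Sample Size and Power).** 20 patients and 20 caregivers. The plan does not say whether this counts those who consent, start or finish.

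**The concern.** A screen failure is ordinarily someone found not to qualify. Section 6e uses the term for anyone who consents, answers the questionnaires and then leaves before the intervention, whatever the reason. Because eligibility is checked at the Screen step, many of these people will have qualified, and their leaving looks more like withdrawal. Section 6d, whose heading covers withdrawal, contains only confidentiality text, so the plan offers no other category for them.

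If a team applied the label and then treated screen failures as outside the study, early losses would be missing from the attrition figure and retention would look better than it was. Retention appears in the monthly progress reports (Section 7a), and the Safety Monitoring Committee may recommend stopping if recruitment or retention becomes futile (Section 10).

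**Working it through.** **What the plan fixes and what it leaves open**

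| Question | Where | Answer |
|---|---|---|
| Who is labelled a screen failure? | 6e | Anyone leaving between consent and the intervention |
| Is the reason recorded? | 6e | Yes, and earlier data are kept |
| Are screen failures left out of retention/attrition? | 6e, 7a, 8 | Not stated |
| Are they replaced, or counted toward the 20? | 6a, 8 | Not stated |
| Does any outcome use retention? | 7, 8 | No |
| Is there a numeric retention threshold? | 10 | No |

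The feared understatement needs two rules. Section 6e supplies the first, the label. The second, that labelled subjects are dropped from the attrition count, appears nowhere.

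**Size if the second rule were applied anyway**

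The plan has no retention figure to reproduce. The only documented input is 20 dyads. Early exits *k* and later losses *m* are assumptions: *k* = 1 to 3 and *m* = 2. Intervals are exact (Clopper-Pearson) 95%.

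If 20 consent and exits are not replaced, retention over all consented dyads is (20 − k − m)/20; leaving out early exits it is (20 − k − m)/(20 − k).

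| k | All consented | Early exits left out | Gap (points) |
|---|---|---|---|
| 1 | 17/20 = 85.0% (62.1–96.8) | 17/19 = 89.5% (66.9–98.7) | 4.5 |
| 2 | 16/20 = 80.0% (56.3–94.3) | 16/18 = 88.9% (65.3–98.6) | 8.9 |
| 3 | 15/20 = 75.0% (50.9–91.3) | 15/17 = 88.2% (63.6–98.5) | 13.2 |

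If exits are replaced until 20 start, the two figures are (20 − m)/(20 + k) and (20 − m)/20.

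| k | All consented | Early exits left out | Gap (points) |
|---|---|---|---|
| 1 | 18/21 = 85.7% | 18/20 = 90.0% | 4.3 |
| 2 | 18/22 = 81.8% (59.7–94.8) | 18/20 = 90.0% (68.3–98.8) | 8.2 |
| 3 | 18/23 = 78.3% | 18/20 = 90.0% | 11.7 |

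With k = 0 the two figures are the same. The intervals overlap heavily in every pair shown. That overlap does not excuse a wrong denominator, but it shows how little a retention percentage from 20 dyads can settle.

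**How long the window is**

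Recruitment is within 10 days of admission (Section 6). In Table 5 of Section 9, goal-setting can begin on day 2 and the planning meeting falls on days 5 to 10. If those days run from admission, which is an assumption, a dyad consenting on day 1 whose first contact is the meeting on day 10 has 10 − 1 = 9 days in which to leave. A dyad consenting after goal-setting has begun has none.

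**What it could reach**

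The eight feasibility items measure delivery by staff, for which dyads who started are a defensible denominator. Acceptability and the secondary outcomes come from interviews after discharge, and people who left before the intervention are not followed. Those results are the same under either retention denominator. The committee's stopping criterion names recruitment and retention together, so an early exit counted under either heading still bears on the same criterion.

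**The case for a change.** The best case for a change is that the label is wrong in ordinary usage, nothing elsewhere corrects it, and the repair is cheap. Section 7a itself treats dropout and failure to meet entry criteria as different matters, while Section 6e gives one name to both. A reader of a report that lists screen failures would assume ineligibility. A few sentences would prevent that without new data.

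Much of this stands as a comment on wording. The label is loose, the retention denominator is unstated, and the reference to a control does not fit a single-arm study. That last point is a clerical slip and has no bearing on attrition.

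The step from loose wording to misleading results does not stand. Because the reason for exit is kept, ineligible and voluntary exits remain distinguishable in the data; only the name is shared. Nor is a split into eligible and ineligible exits as clean as it sounds. Section 5d makes a goal of discharge home and a willing caregiver entry criteria, and both can change after screening. A dyad whose caregiver changes their mind has withdrawn and also no longer meets a condition of entry. A tabulation by recorded reason describes such cases better than a two-way classification, and Section 6e already retains what that needs.

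**Conclusion.** The observation about the label is correct, but it does not call for a change to the plan. This is missing detail about one descriptive figure that is not an outcome, and the records needed to report it properly are kept. An analyst describing recruitment and attrition under Section 8 can show consented dyads, those who left before the intervention with their reasons, those who started, and those lost later.

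On the assumed counts (1 to 3 early exits, 2 later losses), the most unfavourable reading would overstate retention by about 4 to 13 percentage points. That needs exits to occur in a short window and a reporting rule that the plan does not contain. The feasibility, acceptability and secondary outcome results would be unchanged, and no numeric decision threshold depends on the retention figure.

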### 7. STUDY EVALUATIONS AND MEASUREMENTS

#### Data Collection Procedures

The research coordinator (RC) will administer baseline enrollment surveys to collect measures of co-variates while the person with ADRD is in the SNF, or from the caregiver or legally authorized representative of the person. Second, the RC will collect outcome data by phone from persons with ADRD and caregivers in 7, 21, and 30 days after SNF discharge. Finally, also using procedures from the parent study, after a patient's discharge from the SNF, the RC will use a standardized tool to abstract data from the medical record in the SNF and the RC will audit the log maintained by the dementia caregiving specialist (study staff) who will make the caregivers calls after the patient discharges from the SNF.

#### Variables that will be abstracted from medical charts

Patient data collected from SNF medical records include: age, sex, race, ethnicity, health insurance status (Medicare/Medicaid Advantage/Medicare fee-for-service/private), living arrangements before index hospitalization, educational attainment, medical history (primary diagnosis in the hospital discharge summary, hospital care (critical care, surgery and length of stay), depression (Minimum Data Set section D), function (Minimum Data Set section GG), cognitive status (Minimum Data Set section C or the CPS score, SNF care (i.e., SNF length of stay, urgent or acute treatment while in the SNF), discharge destination. Using the problem list in the medical record, we also will calculate the Charlson Comorbidity Index scores for each patient.

#### Variables that will be abstracted from the intervention log maintained by the dementia caregiving specialist (study staff)

As part of Connect-Home Plus, a dementia caregiver specialist will maintain a written log of details from supportive calls with the caregiver after the patient transfer from SNF to home, including one post-discharge support call within 72 hours after discharge and two additional calls within one month of discharge. Data collected from the Call-back log will include: number of days after discharge on which the call occurred, duration of the call, transition challenges identified on the call, caregiver education provided on the call, and follow-up actions and next steps identified on the call.

#### Baseline evaluation

Patient data collected in person or from the caregiver representing the person with ADRD who cannot participate in data collection: frailty (Study of Osteopathic Fractures Index),(28) and social support (ENRICH Social Support Inventory).(29) Caregiver data collected in person or by phone: age, sex, relationship to patient, living arrangements, education, employment, and number of days per week providing patient care.

#### Outcome Measures

- Primary Outcome Measures:

- Number of participants for whom the intervention components were feasible. Feasibility will be measured using an instrument to audit skilled nursing facility medical records of the patient and the intervention log of services for the patient.(1) It includes eight dichotomous (yes-no) items that indicate feasibility of the Connect-Home Plus intervention. The feasibility items include: (1) completing the Transition Plan of Care; (2) convening the care plan meeting with caregiver attending; (3) reviewing advance directives in the SNF; (4) scheduling follow-up medical appointments; (5) transmitting records to follow-up clinicians; (6) home care nurse completion of the first home visit within 24 hours after discharge; (7) completion of first caregiver support call within 72 hours of discharge; (8) completion of the second and third caregiver support call within one month of discharge. A "Yes" answer indicates that the intervention component was feasible to provide for the patient and caregiver dyad.
- Mean patient intervention satisfaction scores. This interview guide will be used to assess the acceptability of Connect-Home Plus with persons with ADRD. The interview will include questions about (1) factors that made the Connect-Home Plus transitional care services easy or difficult to use, (2) specific supports that were and were not helpful, (3) the effect of Connect-Home Plus on how to manage issues related to ADRD at home, and (4) unmet needs for care of issues related to ADRD at home.(1) Responses to the interview guide questions will be used to generate 3 4-point Likert scale acceptability scores, including (how helpful was Connect-Home Plus, (2) how difficult were these services to use, and (3) how well did these services prepare you for care at home. The scores will include 0 meaning not applicable, and scores 1-3 indicating acceptability, with lower scores indicating higher acceptability.
- Mean caregiver intervention satisfaction scores. This interview guide will be used to assess the acceptability of Connect-Home Plus with caregivers of persons with ADRD.(1) This interview guide will include questions about (1) factors that made the Connect-Home Plus transitional care services easy or difficult to use, (2) specific supports that were and were not helpful, (3) the effect of Connect-Home Plus on how to manage issues related to ADRD at home, and (4) unmet needs for care of issues related to ADRD at home. Responses to the interview guide questions will be used to generate 3 4-point Likert scale acceptability scores, including (how helpful was Connect-Home Plus, (2) how difficult were these services to use, and (3) how well did these services prepare you for care at home. The scores will include 0 meaning not applicable, and scores 1-3 indicating acceptability, with lower scores indicating higher acceptability

- Secondary Outcome Measures

- Care Transitions Measure-15. The patient's preparedness for discharge will be measured by the Care Transitions Measure-15 (CTM-15), which includes 5 items on a 4-point scale.(30) The CTM-15 measures self-reported knowledge and skills for continuing care at home. Summary score range 0-100, with higher scores associated with less acute care use after discharge.
- Preparedness for Caregiving Scale. The caregiver's preparedness for caregiving will be measured by the Preparedness for Caregiving Scale (PCS), which includes 8 items on a five-point Likert scale (0-4).(31) The PCS measures self-reported readiness for caregiving. Range = 0-32, with higher scores associated with less anxiety.
- Life Space Assessment. Patient's function will be measured using the Life Space Assessment, which includes 5 Likert scales corresponding to a hierarchy of levels of mobility (each scored from 0-4) where weights are the product of the "Life-space level" (range 1-5) and the "independence" score (range 1-2).(32) The range is 1-120. Lower scores are associated with falls and hospitalization.

- Dementia Quality of Life Measure (patient). The quality of life of the patient will be assessed with the Dementia Quality of Life Measure.(33) It has 28 items that cover four quality of life dimensions: daily activities, memory, negative emotion and positive emotion. The score range is 28-112 with higher scores indicating better quality of life.
- Dementia Quality of Life-Proxy measure (DEMQOL-Proxy). When the patient is unable to rate their quality of life, the quality of life will be rated by their caregiver, using the Dementia Quality of Life-Proxy measure.(33) The score range is 31-124 with higher scores indicating better quality of life.
- Self-Reported Days of ED or Hospital Use 30 Days After Skilled Nursing Facility Discharge. Patient's days of acute care use will be measured using the self-reported number of combined number of days the patients pends in the Emergency Department (ED) or hospital in 30 days after SNF discharge.(19)
- Zarit Caregiver Burden Scale. Caregiver burden will be measured using the Zarit Caregiver Burden Scale, which includes 12 items on a five-point scale, measuring caregiver perceptions that "caregiving has an adverse effect on their emotional, social, financial, physical and spiritual functioning."(34) Scores range 0-48; higher scores are associated with depression and social isolation.
- Distress Thermometer. Caregiver distress will be measured using the Distress Thermometer, which includes 1 item on an 11-point scale, measuring negative affect (e.g., sadness and fear) related to caregiving for a severely ill person. Score ranges 0-10, with scores >4 associated with poor coping and depression.(35)

a. Safety Evaluations

- Study progress and safety will be reviewed monthly (and more frequently if needed). Progress reports will include patient and caregiver recruitment, retention/attrition, and adverse events. In addition, safety evaluation will include (1) whether adverse event rates are consistent with pre-study assumptions; (2) reason for dropouts from the study; (3) whether all participants met entry criteria; (4) whether continuation of the study is justified on the basis that additional data are needed to accomplish the stated aims of the study; and (5) conditions whereby the study might be terminated prematurely.
- An adverse event (AE) is any untoward medical occurrence in a subject temporally associated with participation in the clinical study or with use of the experimental agent being studied. An adverse finding can include a sign, symptom, abnormal assessment or any combination of these. A Serious Adverse Event (SAE) is any adverse event that results in one or more of the following outcomes:
  - Death
  - A life-threatening event
  - Inpatient hospitalization
  - A persistent or significant disability/incapacity
  - Important medical event based upon appropriate medical judgment

Potential sources of information for identification of AEs include (but may not be limited to) nursing home staff reports of events while the patient is in the nursing home, and patient or caregiver reports of events while the patient is in the nursing home or at home. For example, the proposed study team will be in contact with the patient and caregiver over 30 days after the patient discharges from the nursing home to home. We will be calling the patient and caregiver at 7, 21 and 30 days. Any event that is discovered will be immediately relayed to the PI, or if he is away, another member of the research team so that we can execute safety plans and reporting plans described here.

AEs will be labeled according to severity, which is based on their impact on the patient. An AE will be termed 'mild' if it does not have an impact on the patient, 'moderate' if it causes the patient some minor inconvenience

and ‘severe’ if it causes a substantial disruption to the patient’s well-being. AEs will be categorized according to the likelihood that they are related to the study intervention. Specifically, they will be labeled either definitely, probably, possibly or unrelated to the study intervention. If any IRB actions occur, the PI will email a report within 24 hours for the Independent Monitor, the second Independent monitor, and the Program Officer in the NINR in accordance with requirements.

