#### Risks

**Physical Risks:** Patients and caregivers will receive transitional care in the SNF and in the patient's home. Transitional care activities involve verbal assessments, conversation, education, and planning. There is a possibility that participants could be fatigued from participation in the data collection activities. For example, while participating in a care-planning meeting, a patient might feel fatigued or need to take a break. Protection: If any participant has a physical injury, the study team will help them seek immediate medical attention. If a SNF patient or caregiver expresses fatigue during data collection, the data collection session will be terminated immediately, and a follow-up appointment scheduled.

**Psychological Risks:** Emotional distress related to learning more about medical and functional challenges and plans for care at home is a potential psychological risk. Staff in the SNF and in the home after discharge will engage patients and caregivers in conversations to plan strategies for managing illness at home. Also, during enrollment and data collection activities, staff will assess the patients' quality of life, functional mobility, falls at home, days at home without acute care use and caregivers' burden and distress related to the caregiving role. These study-related activities may also involve a chance for emotional distress. Protection: The study team will refer distressed patients and caregivers to their attending or primary care physicians for support with emotional distress.

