**c. Enrollment and Number of Subjects**

20 persons with ADRD and their 20 caregivers in 2 SNFs

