## 10 SAFETY MANAGEMENT

To assure that the study meets expectations and any risk to participants is reduced to a minimum, the proposed study will use the Executive Committee and Safety Monitoring Committee (SMC) that was created in the parent study (Connect-Home Clinical Trial [R01NR017636]).

Executive Committee. The Executive Committee of the parent study will oversee the conduct of the study. The PI will chair the committee, which will meet quarterly, or more often as warranted, to review the activities of the study including management, personnel, recruitment, performance, and any emerging problems.

Safety Monitoring Committee (SMC). The SMC has seven members. The members of the Executive Committee and two members of the committee who will be independent of the protocol. Despite usual precautions, we are aware that adverse events may occur and this committee will monitor the occurrence of adverse events and the overall risk of the study to SNF patients, caregivers and staff. We will develop a system to test whether abnormalities are equally distributed between the intervention and control groups. Data will be presented to the committee if a significant increase in abnormalities is noted. The SMC will use the following stopping rules: (1) the intervention is associated with adverse effects that significantly impact the risk-benefit ratio, (2) study recruitment or retention becomes futile, (3) any new information becomes available during the trial that necessitates stopping the trial; or (4) other situations occur that might warrant stopping the trial. They will use these standards before they recommend modification or premature termination of the study on the basis of safety. Additionally, standards for discontinuing subjects from the study due to related adverse events will be established. The SMC will provide the PI with recommendations regarding problems that would require premature termination of the study for safety reasons. Minutes of each meeting will be kept, and all actions and decisions documented to establish an audit trail. The committee will also provide the PI with advice on whether there is any reason to change the design of the study.

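### Adverse-event severity is defined only by impact on the patient, so a caregiver's event is never graded on the caregiver's own condition and is labelled 'mild' if the patient is unaffected

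*Combined protocol and SAP*

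**What the plan says.** The grading rule is in Section 7, Safety Evaluations: "AEs will be labeled according to severity, which is based on their impact on the patient". The lowest grade reads "An AE will be termed 'mild' if it does not have an impact on the patient". The middle grade is minor inconvenience to the patient. The top grade applies "if it causes a substantial disruption to the patient’s well-being".

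Other parts of the protocol treat caregivers as people whose own harm counts:

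- Section 5c sets enrolment at "20 persons with ADRD and their 20 caregivers in 2 SNFs", and Section 5d gives caregivers their own eligibility criteria.
- Section 7 defines the event by reference to a subject, not a patient: "An adverse event (AE) is any untoward medical occurrence in a subject temporally associated with participation in the clinical study".
- Section 3 (Psychological Risks) covers patients and caregivers together. Of the enrolment and data collection activities, which include asking caregivers about burden and distress, it says "These study-related activities may also involve a chance for emotional distress".
- Section 10 says of the Safety Monitoring Committee that "this committee will monitor the occurrence of adverse events and the overall risk of the study to SNF patients, caregivers and staff".

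Section 8 (Statistical Methods) promises descriptive statistics for adverse events and does not say how they will be broken down.

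**The concern.** A severity grade should describe how bad an event was for the person who had it. Here the definition of an adverse event and the committee's remit both include caregivers, but the scale refers to someone else. The mismatch is foreseeable in this study. The dementia caregiving specialist's calls are directed to the caregiver, and emotional distress is a named risk for caregivers. An event of that kind can be substantial for the caregiver and leave the patient untouched.

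At stake is whether the severity labels on caregiver events mean anything. They would feed any descriptive summary by severity and would be before those who carry out the monthly safety review and the committee. An adverse-event form used in a pilot may also be carried into the later efficacy trial that Section 3 (Potential Benefits) anticipates.

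**Working it through.** There is no figure in the plan to reproduce, so the check is to apply the rule as written and compare it with the rest of the safety text.

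**Step 1. Does 'patient' mean any participant here?** No. Just before the grading rule, Section 7 describes contact with the patient and the caregiver as two people. The protocol keeps that distinction throughout.

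**Step 2. Are caregiver events adverse events?** Yes. The definition applies to a subject, and Section 5c counts caregivers among the subjects.

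**Step 3. Apply the three grades to a caregiver's event.**

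| Effect of the caregiver's event on the patient | Grade under Section 7 | Does the caregiver's own condition enter? |
|---|---|---|
| None | Mild | No |
| Minor inconvenience | Moderate | No |
| Substantial disruption of well-being | Severe | No |

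The last column is 'No' in every row. In the first row, marked distress after a care-planning meeting that does not touch the patient is mild. In the third row, a slight injury to the caregiver that seriously upsets the patient's care is severe. The label can therefore be wrong in either direction.

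**Step 4. Is there another scale for caregivers?** None appears in Sections 2, 3, 7, 8 or 10.

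**Step 5. What share of participants is affected?** Caregivers / all enrolled = 20 / (20 + 20) = 50%.

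**Step 6. What depends on the grade?**

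- Serious adverse events are defined in Section 7 by outcome (death, threat to life, hospitalisation, disability, important medical event), not by grade.
- Section 7 has any discovered event relayed at once to the principal investigator or a deputy.
- Section 10 requires immediate reporting of serious events and deaths, with no condition on grade or on who was affected.
- The stopping rules in Section 10 do not mention severity grade.

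The effect is therefore confined to the severity label itself and to any summary or review that uses it.

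**The case against.** The strongest reply is that the wording does little harm. Caregivers are enrolled because they help the patient at home, so a major caregiver event will often affect the patient and be graded moderate or severe. Serious events are recognised by outcome and reported whatever the grade. The stopping rules do not rely on severity, and the committee is charged with caregiver risk directly. Section 8 does not promise a table by severity. The study is a descriptive pilot of 20 dyads with minimal expected risk.

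All of this stands, and it rules out several stronger readings that a reader might infer:

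- **That every serious caregiver event is graded mild.** Only an event with no impact on the patient is. Seriousness and severity are also separate classifications.
- **That serious caregiver events would be missed or reported late.** No capture, relay or reporting step uses the grade.
- **That the committee's risk-benefit review is wrong for half the participants.** The 50% is the share of participants without a grade of their own. It is not a share of wrong decisions.
- **That a number of mislabelled events can be stated.** This would need a caregiver event rate and the proportion of those events that leave the patient unaffected. The documents give neither.
- **That the Distress Thermometer should trigger adverse-event recording.** Section 7 says "Score ranges 0-10, with scores >4 associated with poor coping and depression", but that describes the score. How scores enter event recording is a separate question. No baseline score is scheduled, so a high value could reflect distress present before the study.

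The reply does not remove the contradiction between the grading rule and the definition and remit around it.

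**Conclusion.** The point holds as a contradiction in the text, not merely a missing detail: a stated rule, followed literally, gives the wrong label. The severity scale in Section 7 cannot grade a caregiver's event by its effect on the caregiver, and it labels as mild any caregiver event that leaves the patient unaffected. It applies to 20 of 40 enrolled participants (50%). The number of events involved is unknown. The consequence is limited to severity labels in descriptive summaries and in material available for safety review.

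The conclusion assumes that 'patient' in the grading rule has the meaning it has elsewhere in the protocol, and that staff follow the rule as written. Staff might in practice grade caregiver events on the caregiver's condition, but nothing in the documents tells them to, so grading could differ between coordinators. The point is worth correcting before the adverse-event form is used. It does not threaten the study's conduct.

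**What to change.** In Section 7, Safety Evaluations, replace 'the patient' with 'the affected participant (patient or caregiver)' in the sentence that sets the basis for severity and in each of the three grades. In Section 8, Safety Analysis, state that adverse events will be summarised separately for patients and caregivers. The grading rule then agrees with the definition of an adverse event in Section 7 and with the committee's remit in Section 10.

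The cost is a short wording amendment, a matching change to the adverse-event form, and one more column in the summary. Some caregiver events will be recorded as moderate or severe that would otherwise have been mild, which is the purpose of the change. Sample size, endpoints, intervention and serious-event reporting are unaffected.
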